6.3.1 Study Schedule

Subject time devoted to this study will be the reviewing and signing the informed consent.

The timepoints for involvement in the study will be:

1. The process of informed consent for patient/sperm source dyads
2. The oocyte retrieval- After retrieval in the event that there are 6 or more mature oocytes, the couple will be enrolled into the study
3. The sperm separation- The sample will either be obtained via fresh production from sperm source the day of oocyte retrieval or will be cryopreserved sperm. The sample will be assessed the day of oocyte retrieval and if the sperm sample is sufficient, it will be processed via ZyMot and density gradient. Following processing of the sperm sample, in the event that there are 6 mature oocytes available to inseminate, the patient will be enrolled into the study. Oocytes will be randomized to insemination via density gradient separated sperm and ZyMot separated sperm.
4. In the event that the orders were written for ICSI per embryologist, if the patient does not meet criteria for IVF the day of oocyte retrieval (as per section 6.3), the oocytes will be inseminated via IVF with density separated sperm only, however, the pre and post sperm parameters following ZyMot separated sperm and density gradient separated sperm will be recorded as per our secondary objectives. Similarly, in the event that there are less than 6 mature oocytes, the oocytes will only be inseminated via density gradient separated sperm, however, pre and post sperm parameters following ZyMot separated sperm and density gradient separated sperm will be recorded as per our secondary objectives. Insemination- Following oocyte retrieval, those enrolled into the study will have their oocytes split and inseminated with ZyMot separated sperm and density gradient separated sperm.
5. Fertilization check- Approximately 16-18 hours following insemination the embryos will be assessed for fertilization.
6. Five and 6 days following insemination, the embryos will be assessed for stage of growth and those reaching blastocyst stage will be given a morphological grade.
7. In the event that patient will undergo a fresh transfer the patient will be transferred 5 days following oocyte retrieval. In the event that pre-implantation genetic testing is performed or the embryos are cryopreserved for any other reason, the patient may undergo a frozen embryo transfer in standard fashion.
8. Nine days following embryo transfer, the patient will follow up for a pregnancy test. In the event its is positive, the patient will follow up approximately 2-3 days later for a repeat pregnancy test. Depending on the value, the patient will either follow up again for a pregnancy test or follow up approximately 1 week later for an ultrasound. In the event of a normal intrauterine pregnancy, the patient is generally referred to her Obstetrician for obstetric care.

As per our standard of care, patients will be contacted by embryology staff via phone after their expected due to date for their pregnancy outcome. Pregnancy outcomes will be recorded in the patient's medical record.

6.3.2 Informed Consent

Consent and other informational documents provided to participants consent forms describing in detail the study agent, study procedures, and risks are given to the participant and written documentation of informed consent is required prior to starting intervention/administering study product.

Consent procedures and documentation informed consent is a process that is initiated prior to the individual's agreeing to participate in the study and continues throughout the individual's study participation. Extensive discussion of risks and possible benefits of participation will be provided to the participants. Consent forms will be IRB-approved and the participant will be asked to read and review the document. All discussions about this research with patient/sperm source dyads will occur in private consultation offices, exam rooms, or a secure WebEx platform. The patient/sperm source dyad will have the consent emailed to the patient/sperm source dyad to be signed during the WebEx meeting or in person. The study investigator and or research assistant will explain the study protocol and details of the patient/sperm source's role and anticipated experience during the procedure, allowing the patient/sperm sources to ask questions, which will be answered to the subject's satisfaction. The consentor will also ask questions of the prospective patient/sperm sources to assess that they have understood the information presented to them. The participants should have the opportunity to discuss the study with their relatives or think about it prior to agreeing to participate. The patient/sperm sources will sign the informed consent document prior to any procedures being done specifically for the study. The investigator or research assistant who obtained consent will sign the consent form. A signed copy of the consent form will be provided to the patient/sperm source dyad. The day of the oocyte retrieval, the sperm will be processed as explained above and used to inseminate the oocytes with both sperm processed using the density gradient and ZyMot microfluidics as long as they are eligible for inclusion. Subjects can withdraw from the study at any time if they no longer wish their data to be collected and used for study purposes. However, they will be informed that if they withdraw after insemination, the insemination process cannot be reversed. The rights and welfare of the participants will be protected by emphasizing to them that the quality of their medical care will not be adversely affected if they decline to participate in this study.

If, during this interview, it becomes apparent that the prospective patient / sperm source dyad lacks sufficient knowledge and comprehension of the information represented by the elements of informed consent to enable them to make an informed and enlightened decision on whether or not to participate in the study, they will be excluded from participating in the study.

A copy of signed informed consent document will be obtained and stored in a binder locked in the investigators' office. The consent process, including the name of the individual obtaining consent, will be thoroughly documented in the patient/sperm source dyad's research record. Any alteration to the standard consent process (e.g., use of a translator, consent document presented orally, etc.) and the justification for such alteration will likewise be documented.

See attached informed consent.

6.3.3 Screening

All patients/donor dyads potentially undergoing ICSI and meeting inclusion criteria for the study will be approached to participate in the study. Screening will be performed by study investigators at NYU Langone Reproductive Specialists of NY.

6.3.4 Recruitment, Enrollment and Retention

Recruitment into the study will be performed by a study investigator at NYU Langone RSOFNY. Patient/sperm source dyads are recruited from the study investigators' practice (RSOFNY) during a routine clinical visit. If patient/sperm source dyads desire to enroll in the study, it will be denoted in their medical record chart. If they meet eligibility criteria on the day of oocyte retrieval (no evidence of severe male factor infertility or surgically derived sperm, at least 6 mature oocytes available for randomization, and possibility for ICSI insemination) the study will be performed as per study protocol.

In the event that the patient consented to the study but the provided semen sample on the day of oocyte retrieval shows severe male factor infertility. The patient/sperm source dyad will then be withdrawn from the study since the sample will not qualify for preparation via ZyMot nor density gradient.

In the event that the patient/sperm source dyad consented to the study but does not meet the inclusion criteria of ICSI insemination or at least 6 mature oocytes available for insemination, insemination will occur only with the sperm separated via density gradient, however, the sperm parameters following ZyMot and density gradient sperm separation will be recorded. The data on sperm parameters after sperm separation via ZyMot and density gradient will still be collected but the patient/sperm source dyad will have no further participation in the study.

6.3.5 On Study Visits

Not applicable.

6.3.6 End of Study and Follow-up

If the patient/donor dyad is enrolled into the study, the primary and secondary data endpoints will be documented as they become available.

No further follow up for those subjects withdrawn from the study will be needed as they will undergo ART procedures as per our standard of care.

6.3.7 Removal of subjects

Following enrollment into the study, the patient/sperm source dyads may withdraw from the study at any point prior to insemination of the oocytes.

In the event that the patient/sperm source dyad consented to the study but the provided semen sample on the day of oocyte retrieval shows severe male factor infertility as per above criteria, the patient/sperm source dyad will be withdrawn from the study since the sample will not qualify for preparation via ZyMot nor density gradient.

In the event that the patient/sperm source dyad consented to the study but does not meet the inclusion criteria of ICSI insemination or at least 6 mature oocytes available for insemination, insemination will occur only with the sperm separated via density gradient, however, the sperm parameters following ZyMot and density gradient sperm separation will be recorded. The data on sperm parameters after sperm separation via ZyMot and density gradient will still be collected but the patient/sperm source dyad will have no further participation in the study.

6.4 Statistical Method

6.4.1 Statistical Design

All data will be de-identified and then will be analyzed by a statistician. Descriptive statistics of the study sample will be calculated (mean \pm standard deviation or median [25th, 75th percentiles] for continuous variables; frequency and percent for categorical data. Paired analyses will be performed. A result will be considered statistically significant at the $p < 0.05$ level of significance. All analyses will be performed using SAS version 9.4 (SAS Institute Inc., Cary, NC).

6.4.2 Sample Size Considerations

For a two-tailed McNemar's test with alpha level 0.05, the following relation yields an approximate power of 80% to detect a difference d between proportions p_1 and p_2 : $n = \frac{16pq(1-r)}{d^2}$ where n is the size of the sample (i.e. number of eggs), $p = (p_1 + p_2)/2$, $q = 1 - p$, $d = |p_2 - p_1|$, and r is the phi

correlation coefficient¹. We will assume a conservative estimate for the correlation $r=0.5$. Assuming a 48% good quality blastocyst development rate and a 7% improvement in good quality blastocyst development with ZyMoT, we would need a total of 408 oocytes randomized to either density gradient or ZyMoT separation, which would equate to 68 patient/sperm source dyads each with ≥ 6 eggs retrieved.

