The study will be completed once 408 oocytes are randomized, which is anticipated to be in approximately 1-2 years.

Study Design

Subjects meeting inclusion criteria will be approached for inclusion into the study and informed consent will be obtained from the patient and the sperm source. Controlled ovarian hyperstimulation will be performed followed by oocyte retrieval as per our standard protocol. On the day of oocyte retrieval, sperm samples will be split into two samples and processed via density gradient (our standard sperm separation technique) and ZyMot (our experimental arm). Sperm parameters will be evaluated pre and post-sperm separation following ZyMot and density gradient. Following oocyte retrieval, the oocytes will be assessed as per our standard fashion. In the event that the oocytes will be inseminated via intracytoplasmic sperm injection (ICSI) and there are 6 or more mature oocytes, half of the oocytes will be inseminated via ZyMot processed sperm and half with sperm processed via density gradient. In the event that there are less than 6 mature oocytes or the insemination technique will be IVF, the oocytes will only be inseminated with sperm processed via density gradient. Additionally, in the event that the sperm sample is insufficient for ZyMot processing (<0.5 million total motile sperm and/or no sperm observed with progressive forward motility), the sperm will not be processed with ZyMot and the patient will be withdrawn from the study.

The primary outcome will be percentage of good quality embryo formation resulting from oocytes inseminated following ZyMot separated sperm compared to density gradient separated sperm. Secondary outcomes will include percentage of euploid embryos in the

event that PGT-A is performed, pregnancy rates, miscarriage rates, live birth rates, and sperm parameters following sperm processing. Decision to transfer an embryo will be made as per our standard protocols regardless of the sperm processing technique.

Study Population

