- Following oocyte retrieval, oocytes will be denuded of their cumulus cells per standard protocol. If at least 6 mature oocytes (determined by visualization of a polar body) are present, half the oocytes will be ICSI inseminated with sperm prepared via ZyMot device and half will be ICSI inseminated with sperm prepared with density gradient. Patients whose patient identification number (PID) is even will have the group of oocytes inseminated with sperm separated via ZyMot device recorded first in the eMR gamete sheet (beginning with oocyte #1.) Patients with an odd PID will have the oocytes inseminated with sperm separated via density gradient recorded first in the eMR gamete sheet (beginning with oocyte #1.) In the event of an odd number of oocytes, the patients with even PIDs will have the extra oocyte inseminated with sperm separated via Zymot device and patients with odd PIDs will have the extra oocyte inseminated with sperm separated via density gradient. Inseminated oocytes will be grouped into separate wells of a LifeGlobal 4 well GPS dish (Cooper Surgical) by the sperm separation method — one well will contain all oocytes inseminated with sperm selected by ZyMot device and a separate well will contain all oocytes inseminated with sperm selected by density gradient centrifugation.

Control Group of Oocytes:

Half of the eggs will be inseminated via ICSI using sperm selected by conventional gradient centrifugation.

Treatment Group of Oocytes:

- Half of the eggs will be inseminated via ICSI using sperm selected using ZyMot.
- Fertilization assessment will be performed between 16 and 18 hours after insemination and normal fertilization will be considered visualization of exactly two pronuclei. Normally fertilized oocytes (embryos) will then be cultured in Continuous Single Culture Medium — NX Complete (Irvine Scientific) in separate, numbered droplets in LifeGlobal microdrop GPS dishes (Cooper Surgical.) The numbers of the droplets will correlate to oocyte/embryo number in the eMR gamete sheet and, thereby, also correlate to the type of sperm used for the insemination. Development of the embryos will be assessed on culture days 5 and 6 and embryo stage and grade will be recorded for each embryo.

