7.15 Study Completion

Study will be completed when 408 oocytes are randomized which is anticipated to be in approximately 1-2 years from study commencement.

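### r = 0.5 is called conservative, but in the plan's formula it halves n from 816 (at r = 0) to 408 with no stated basis; the 204 pairs that 408 oocytes form need r of about 0.75 for 80% power

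*Combined protocol and SAP*

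**What the plan says.** Section 6.4.2 (Sample Size Considerations) opens with "For a two-tailed McNemar's test with alpha level 0.05" and states that "the following relation yields an approximate power of 80% to detect a difference d between proportions", giving n = 16pq(1-r)/d². There p is the mean of the two proportions, q = 1 - p, d is their difference and r is the phi correlation; n is described as a number of eggs. The next sentence reads "We will assume a conservative estimate for the correlation" and sets r = 0.5. With a 48% control rate and a 7-point improvement, the section arrives at "a total of 408 oocytes randomized to either density gradient or ZyMoT separation", equated to 68 dyads with at least 6 eggs each.

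The same count is the stopping rule. The Synopsis (Study Duration) says "The study will be completed once 408 oocytes are randomized", and section 7.15 says "Study will be completed when 408 oocytes are randomized". Under section 6.1.2, "half the oocytes will be ICSI inseminated with sperm prepared via ZyMot device", and the other half with density-gradient sperm; section 6.1.3 repeats this. Section 6.4.3.1 names McNemar's test as the primary analysis.

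A footnote attached to the phi coefficient cites a paper on a crude sample-size formula for McNemar's test. Nothing in the protocol gives a source, pilot estimate or range for the value 0.5.

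**The concern.** An assumption is conservative when an error in it is likely to leave the trial larger than needed. Here n is proportional to (1 - r), so a higher r makes the trial smaller and a lower r is the cautious choice. Setting r = 0.5 removes half the sample that the same formula requires at r = 0. It could be called conservative only relative to an expected value above 0.5, and the protocol gives none.

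The label makes the 80% power claim read as if it carried a safety margin, when the claim depends on one unsupported input. If the real correlation is lower than the design needs, a non-significant result could reflect low power and be misread as no benefit of ZyMot. The exposure is greater because the planned count is in oocytes while the formula counts pairs.

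**Working it through.** **Inputs (section 6.4.2).** p1 = 0.48; p2 = 0.48 + 0.07 = 0.55; d = 0.07; p = (0.48 + 0.55)/2 = 0.515; q = 0.485; pq = 0.249775; two-sided alpha 0.05; target power 80%; r = 0.5. Total oocytes: 408.

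**1. Reproduce the plan's figure.** 16 × 0.249775 × (1 - 0.5)/0.07² = 407.8, rounded up to 408. This matches, so the 7% is an absolute difference.

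**2. Direction of r.** At r = 0 the formula gives 16 × 0.249775/0.0049 = 815.6, rounded up to 816. Every increase in r lowers n, and r = 0.5 halves it.

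**3. What n counts.** The variance of a paired difference over n pairs is about 2pq(1-r)/n. The required n is therefore (1.96 + 0.84)² × 2pq(1-r)/d², and 2 × 2.80² = 15.7, which the formula rounds to 16. So n is a number of pairs. As a cross-check, the usual normal-approximation McNemar calculation on the discordant cells implied by 48%, 55% and phi = 0.5 gives 403.6 pairs.

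**4. Pairs available.** 408 oocytes split in half give 408/2 = 204 pairs at most; a patient with an odd number of oocytes leaves one unpaired.

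**5. Power for 48% against 55%.** Power = Φ(d√N/√(2pq(1-r)) - 1.96), with N the number of pairs. At N = 204 and r = 0.5: 0.07 × 14.283/√0.249775 = 2.0005, and Φ(2.0005 - 1.96) = 0.516.

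| r | n from plan's formula | Power, 204 pairs (408 oocytes) | Power, 408 pairs (816 oocytes) | Difference detectable at 204 pairs (plan's 80% formula) |
|---|---|---|---|---|
| 0 | 815.6 | 29% | 52% | 13.9 points |
| 0.2 | 652.5 | 35% | 61% | 12.5 points |
| 0.3 | 570.9 | 39% | 67% | 11.7 points |
| 0.5 | 407.8 | 52% | 81% | 9.9 points |
| 0.6 | 326.2 | 61% | 89% | 8.8 points |
| 0.75 | 203.9 | 81% | 98% | 7.0 points |

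The last column solves 16pq(1-r)/d² = 204 with p1 = 0.48 and p recomputed for each d.

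**6. Check on the approximation.** Full enumeration of the uncorrected McNemar test gives 29.3%, 35.3%, 39.4%, 51.3%, 60.8% and 83.1% with 204 pairs, and 51.6%, 60.6%, 66.5%, 81.0%, 89.0% and 98.4% with 408 pairs, in the same order of r.

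**7. The r that the 80% claim needs.** Solving the plan's formula for r gives 1 - N × d²/(16pq), which is 0.500 for N = 408 and 0.750 for N = 204. The discordant-cell calculation gives 0.494 and 0.751.

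**The case against.** The strongest reply is that a conservative r is one set below the value the authors expect, so 0.5 could be cautious if they expected more. Such values are possible: with margins of 48% and 55%, phi can reach √(0.48 × 0.45/(0.52 × 0.55)) = 0.87. Sister oocytes share a patient and a cycle, which is a reason to expect positive correlation. This stands to a degree: the documents do not show that 0.5 is too high. But they give no expected value, so the label has nothing to rest on. The cited paper could not be consulted. The finding is that the protocol states no basis for 0.5, not that none exists.

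A second reply is that r = 0 is a benchmark the plan never uses, and that any paired design gains from positive correlation. That is fair. The benchmark only shows how much of the sample size depends on r.

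A third is that the 52% at r = 0.5 comes from counting eggs instead of pairs, not from the label. That is true, and it is why both readings are tabulated. Even with 408 pairs, r must be about 0.5 or more.

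Finally, section 5.3.1 reports an average of 12 mature oocytes per eligible cycle and anticipates 138 cycles. That would be 138 × 12 = 1,656 oocytes, or 828 pairs, with about 81% power even at r = 0. The inconsistency is real, but the same section also states a need for 408 oocytes, and the Synopsis and section 7.15 end the study there. It also stands that no section says how an oocyte in one half is matched to one in the other, so r itself is not fully defined.

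**Conclusion.** The concern holds. The plan's arithmetic reproduces, but r = 0.5 is unsupported, and in this formula raising r reduces the sample size instead of protecting it. With 408 pairs, the 80% claim needs r of about 0.5 or more, so the plan's own value leaves essentially no margin. With the at most 204 pairs that 408 oocytes form, it needs r of about 0.75; at r = 0.5, power is about 52% and the difference detectable with 80% power is 9.9 points instead of 7.

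These figures assume 48% against 55%, the uncorrected two-sided McNemar test at 0.05, and independent pairs, as the plan's formula does. The range r = 0 to 0.75 is assumed, because the documents do not give the true value. The statement should be corrected; the documents do not establish that the real correlation is below 0.5.

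**What to change.** In section 6.4.2, delete the word conservative. Give the basis for r = 0.5, or say that it is an unverified assumption. Replace the single 80% figure with power at the number of pairs actually planned, over r on both sides of 0.5. For 408 oocytes as now written, suitable text would be:

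> The correlation r is an unverified assumption. With 408 oocytes split in half (at most 204 pairs), power for 48% versus 55% is about 29%, 35%, 39%, 52%, 61% and 81% at r = 0, 0.2, 0.3, 0.5, 0.6 and 0.75.

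Only if 408 pairs (816 oocytes) are planned should the text give about 52%, 61%, 67%, 81%, 89% and 98%. Those figures must not be presented as the power of a 408-oocyte trial.

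The cost is a text edit and a one-row power table; enrolment and procedures do not change. The downside is a less favourable stated power. Whether to accept that or enlarge the trial is a separate and more expensive decision.

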The study population will include patient/sperm donor dyads where all patients over 18 years of age are undergoing controlled ovarian hyperstimulation for IVF with ICSI using ejaculate sperm and having at least 6 mature oocytes retrieved. The sperm source/donor will provide informed consent for the use of their sperm sample in this research study. The relationship of the sperm source will can be the intended father, a known sperm donor in a same-sex couple or a known donor in the case of a single patient. The identity of the donor cannot be anonymous.

Number of Participants

Following power calculation, 408 oocytes will be needed to randomize (see details in the statistics section). The number of patient/sperm source dyads enrolled will depend on the number of oocytes obtained from each patient. The maximum number of subjects will be 68 (in the event that 6 oocytes were obtained from every patient enrolled in the study).

Number of Study Sites

This study will take place at NYU Langone Reproductive Specialists of NY.

Primary Outcome Variables

The primary outcome of our study is to evaluate whether good quality embryo formation is significantly improved with ICSI following sperm separation using ZyMot compared to density gradient.

Secondary and Exploratory Outcome Variables

The secondary objectives will be to evaluate:

1. Sperm parameters prior to and following sperm separation with ZyMot compared to density gradient
2. Normal fertilization rates following ICSI comparing sperm separation with ZyMot with density gradient
3. Euploid rates, in the event that PGT-A was performed, following ICSI comparing sperm separation with ZyMot with density gradient
4. Embryo transfer results including:
 - a. Not pregnant
 - b. Biochemical pregnancy, defined as BHCG value > 5 mIU/ml without ultrasound evidence of gestational sac within the uterus
 - c. Clinical miscarriage, defined as loss of a pregnancy following a positive BHCG value and ultrasound revealing presence of a gestational sac within the uterus
 - d. Clinical pregnancy, defined as positive BHCG with a gestational sac within the uterus
 - e. Ongoing Pregnancy, defined as a positive BHCG value with ultrasound evidence of intrauterine gestational sac at or past 8 weeks gestation
 - f. Live birth, defined as birth of a baby at 20 weeks or later, showing signs of life, including breathing, beating of the heart, pulsation of the umbilical cord, or definite movement of the voluntary muscles.

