5.3.1 Number of Participants

As this study will be randomizing oocytes, and therefore the number of participants will depend on the average number of oocytes retrieved per patient. Following power calculation, 408 oocytes are needed for randomization in order to detect a significant difference in our primary outcome. If 6 oocytes are obtained from each patient enrolled in the study, then 68 patient/sperm source dyads will be enrolled.

Based on our 2020 data, there was a total of 1,680 mature oocytes from 137 retrievals that produced 6 or more mature oocytes for ICSI insemination, from 121 different patients. The average number of mature oocytes within ICSI cycles with 6 or more mature oocytes obtained was 12 mature oocytes. Based on this data, we anticipate 138 patient cycles are needed for this study and this could include up to 138 patient/sperm source dyads.

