6.1.3 Method of Assignment/Randomization

Patient/sperm source dyads meeting inclusion criteria and enrolled in the study will have their sperm sample prepared prior to or near the time of oocyte retrieval. Semen parameters will be recorded prior to separation. Semen will be split and separated via ZyMot and density gradient.

Following oocyte retrieval, oocytes will be denuded of their cumulus cells per standard protocol. If at least 6 mature oocytes (determined by visualization of a polar body) are present, half the oocytes will

be ICSI inseminated with sperm separated via ZyMot device and half will be ICSI inseminated with sperm prepared with density gradient. Patients whose patient identification number (PID) is even will have the group of oocytes inseminated with sperm separated via ZyMot device recorded first in the eMR gamete sheet (beginning with oocyte #1.) Patients with an odd PID will have the oocytes inseminated with sperm separated via density gradient recorded first in the eMR gamete sheet (beginning with oocyte #1.) In the event of an odd number of oocytes, the patients with even PIDs will have the extra oocyte inseminated with sperm separated via Zymot device and patients with odd PIDs will have the extra oocyte inseminated with sperm separated via density gradient.

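### Section 6.4.2's McNemar formula returns 408 matched pairs, but the plan uses 408 as total oocytes (at most 204 pairs), so power is about 46–51%, not 80%

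*Combined protocol and SAP*

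**What the plan says.** Section 6.4.2 uses n = 16pq(1−r)/d² for a two-tailed McNemar test at alpha 0.05 and about 80% power. It says that n "is the size of the sample (i.e. number of eggs", so n is read as single oocytes. The control rate is 48% and the gain 7%. For r the text says "We will assume a conservative estimate for the correlation" and takes 0.5. The conclusion is that "we would need a total of 408 oocytes randomized to either density gradient or ZyMoT separation", which is equated to 68 dyads, that is 68 × 6 oocytes. The Synopsis (Number of Participants) gives 68 as the maximum "in the event that 6 oocytes were obtained from every patient enrolled in the study".

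The same number ends the trial. The Synopsis (Study Duration) says "The study will be completed once 408 oocytes are randomized", and section 7.15 says "Study will be completed when 408 oocytes are randomized".

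Sections 6.1.2 and 6.1.3 divide each patient's mature oocytes in half between the two preparations. "In the event of an odd number of oocytes, the patients with even PIDs will have the extra oocyte inseminated" with ZyMot sperm; for odd PIDs the extra one goes to density gradient. Section 6.4.3.1 names McNemar's test as the primary analysis.

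Section 5.3.1 repeats 408 oocytes and 68 dyads and reports 1,680 mature oocytes from 137 eligible retrievals in 2020. It then adds that "we anticipate 138 patient cycles are needed for this study", with up to 138 dyads.

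**The concern.** McNemar's test works on pairs: one observation under each method. A McNemar sample-size formula would normally return the number of pairs, and here each pair uses two oocytes. If 408 is a pair count, the plan recruits half of what its own calculation asks for.

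The stake is the primary outcome. The trial would stop in the belief that it had 80% power for a 7-point gain. With power near one half, a non-significant result would be about as likely as a significant one even if the assumed gain were real, and it could be misread as evidence of no benefit.

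**Working it through.** **Inputs (section 6.4.2).** p1 = 0.48, p2 = 0.55, d = 0.07, p = 0.515, q = 0.485, r = 0.5, two-sided alpha 0.05, power 80%. The 7% must be absolute: a relative 7% would give 1,771.

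**The plan's figure.** 16 × 0.515 × 0.485 × 0.5 / 0.07² = 407.8, so 408. The arithmetic reproduces.

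**What n counts.** For McNemar's test, pairs ≈ (z₀.₉₇₅ + z₀.₈₀)² × ψ / d², where ψ is the proportion of discordant pairs and ψ ≈ 2pq(1−r). The constant is therefore 2 × (1.960 + 0.842)² = 15.70, which rounds to 16. So n is pairs. As a second check, at r = 0 the formula gives 16pq/d² = 816, close to the 800 per arm from the usual formula for two independent proportions. It is a per-arm figure, not a total over both arms.

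**Check with the exact cells.**

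- Both good: 0.48 × 0.55 + 0.5 × √(0.48 × 0.52 × 0.55 × 0.45) = 0.3883
- Discordant: 0.55 − 0.3883 = 0.1617 and 0.48 − 0.3883 = 0.0917, so ψ = 0.2535 after rounding
- Pairs for 80% power: (1.96√0.2535 + 0.8416√(0.2535 − 0.0049))² / 0.0049 = 403.6

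**Power at what the plan recruits.** 408 oocytes / 2 = 204 pairs at most. The normal approximation is Φ[(0.07√204 − 1.96√0.2535) / √(0.2535 − 0.0049)] = 0.51. Full enumeration over the discordant pairs gives:

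| McNemar variant | 204 pairs | 408 pairs |
|---|---|---|
| Uncorrected | 51.3% | 81.0% |
| Mid-p | 51.3% | 80.7% |
| Exact | 46.4% | 78.1% |
| Continuity-corrected | 46.0% | 77.9% |

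**Detectable difference at 204 pairs, r = 0.5.** The plan's formula gives √(16 × 0.515 × 0.485 × 0.5 / 204) = 0.099. The exact test needs 0.102.

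**Odd counts (assumption: half of cycles).** The 2020 yield is 1,680 / 137 = 12.26 oocytes per cycle, so pairs per cycle are (12.26 − 0.5) / 2 = 5.88. Then 408 / 12.26 = 33.3 cycles give about 196 pairs and power of 49.7% (uncorrected), 44.7% (exact) or 44.2% (corrected).

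**Lower correlation (assumed range, 204 pairs).** At r = 0.3, power is 39.4% uncorrected and 34.5% corrected. At r = 0 it is 29.3% and 25.7%. The formula's pair requirement rises to 571 and 816.

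**Counts.** 408 / 6 = 68 dyads. At the site mean of 12, 408 / 12 = 34 cycles. The 138 cycles would supply 138 × 6 = 828 oocytes at the minimum, or 138 × 12 = 1,656 at the mean. Neither equals 408.

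**The case against.** The best objection to the headline range is that the plan's formula is the uncorrected large-sample form and section 6.4.3.1 says only McNemar's test. Like for like, the comparison is then 51% against 80–81%; the 46% belongs with 78%. That is fair, and the table keeps the variants apart. Either way about 30 points of power are lost.

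A second defence is that section 5.3.1 already foresees 138 cycles, and 138 × 6 = 828 is close to 816. This does not help, because the Synopsis and section 7.15 complete the study at 408 oocytes whatever the number of cycles. Section 5.3.1 refers to the 2020 data but shows no derivation of 138. It may allow for consented dyads who are never randomized, but the plan does not say so.

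Third, section 6.4.3.2 adds a conditional logistic model with generalized estimating equations, which needs no one-to-one pairing. It is an additional analysis with no sample-size basis. A simulated stratified matched-set analysis of 408 oocytes (34 × 12 or 68 × 6, assumed exchangeable r = 0.5) also gave about 51%.

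Other assumptions do not rescue the figure. One-sided testing at 0.05 would give 63% at 204 pairs, and the plan says two-tailed. The formula gives 204 pairs only if r is about 0.75, for which the plan offers no support. The lower values of r are a sensitivity range and not an arithmetic error by the plan. They do show that 0.5 is not a cautious choice unless lower values can be ruled out.

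**Conclusion.** The concern holds. The number 408 is computed correctly and given the wrong unit. With 408 oocytes in total, power for 48% versus 55% is about 51% (uncorrected) or 46% (exact or continuity-corrected), and 80% is reached only for a difference of about 10 points.

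These figures rest on r = 0.5 and on every oocyte having a sibling partner in the other arm. The plan gives no support for the first and no matching rule for the second, and odd counts leave an oocyte unpaired, so 204 pairs is an upper limit. No allowance for missing outcomes was applied. The mismatch between 68 and 138 dyads is a secondary consistency point; it does not change the power.

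**What to change.** In section 6.4.2:

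- Define n as matched pairs of two oocytes, one per method.
- State that 408 oocytes give at most 204 pairs and roughly 50% power for a 7-point gain, with 80% only for about 10 points.
- State that this depends on r = 0.5 and one-to-one matching. Define the matching, including what happens to the extra oocyte.
- Justify r, or stop calling it conservative, and show power for values below 0.5.

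Reconcile the oocyte and dyad counts in the Synopsis and sections 5.3.1, 6.4.2 and 7.15, and say what the 138 cycles count. All of this is a wording change.

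If the sponsor prefers to keep 80% power for 7 points, the target under the same conditions is about 408 × 2 = 816 oocytes. At the 2020 yield that is 816 / 12.26 = 66.5, so about 67 cycles. If half of cycles have an odd count, 408 pairs need 408 / 5.88 = 69.4, so about 70 cycles; a completion rule stated in pairs would cover this. At 6 oocytes each, the plan's own logic gives 816 / 6 = 136 dyads. That is above the Synopsis maximum of 68 but within the 138 that section 5.3.1 already allows. This option needs a protocol amendment.
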